**Wave 2 Recruitment added to Protocol version 6**

Wave 2 recruitment will recruit the same patient population, at the same recruitment sites as Wave 1. Frequency of follow-up will be adjusted as described in Table 1.

Patient recruitment: 60 patients will be recruited to participate within 30 to 45 days of diagnosis with IBD.

**Table 1. Timeline for Data Collection Aim 1 (n = 120; 60 IBD and 40 control at baseline; IBD patients followed over 24 months)**

Scheduled Assessments	Baseline (IBD and Control)	Month of Follow-up (IBD only)				
		4	8	12	18	24
Patient Report						
Depression: CDI-2	X	X	X	X	X	X
Anxiety: MASC	X	X	X	X	X	X
Stress: PROMIS	X	X	X	X	X	X
Lifetime stress: LITE	X	X	X	X	X	X
Disease symptoms: PedsQL GI Module	X	X	X	X	X	X
Pain Interference						
Parent Report						
Parent Report of Children's Reactivity.	X					
BASC-2						
Psychophysiology						

Skin conductance	X		X		X
Heart rate variability	X			X	
Inflammatory markers					
CRP	X	X	X	X	
Fecal calprotectin	X	X	X	X	
Physical Assessment/Chart Review					
BMI; Height; growth velocity	X	X	X	X	X
PUCAI/PCDAI (IBD pts)	X	X	X	X	X
Clostridium difficile diagnosis history	X	X	X	X	X

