#### 8. Participant selection:

- Waves 1 and 2 of Observational Research:
- Youth ages 8 to 17 years diagnosed with Crohn's disease, ulcerative colitis, or indeterminate colitis within the last 30 days. One parent or primary caregiver will be recruited along with each child. Inclusion criteria will include (1) biopsy confirmed diagnosis of IBD within last 30 days and (2) English fluency for parent and child participants. Exclusion criteria will include (1) documented history or parent report of developmental delay or intellectual disability (2) parent unwilling to participate. Emory University IRB approval will be obtained for all study procedures prior to start of data collection.
- Requested sample size for Wave 1: 60 youth; 10% refusal rate and 10% withdrawal rate expected based on previous research with this sample
- Requested sample size for Wave 2: 60 youth diagnosed with IBD; 10% refusal rate and 10% withdrawal rate expected based on previous research with this sample
- Screening for eligibility of IBD patients will occur through medical records review and in collaboration with doctors/nurses at GI Care for Kids and Egleston Children's Center based on newly diagnosed IBD patients.
- **Inclusion Criteria.** To participate, patients must be (a) Diagnosed with biopsy-confirmed IBD within the last 30 days, (b) ages 8 through 17 years inclusive, (c) speak English, (d) accompanied by at least 1 parent/guardian who is willing to participate. Control participants must meet all inclusion criteria excluding diagnosis with IBD or other chronic health condition.
- **Exclusion Criteria.** Patients meeting any of the following criteria will be excluded from participation: (a) Previous diagnosis of intellectual disability, (b) autism spectrum disorder.
- If a subject withdraws, their previously collected data will be destroyed if requested. Otherwise, previously collected data will remain part of data collected but no further attempts to contact this participant will be made.
- **Intervention: Inclusion Criteria.** To participate, patients must be (a) Diagnosed with biopsy-confirmed IBD, (b) ages 13 through 18 years, (c) speak English, (d) accompanied by at least 1 parent/guardian who is willing to participate, (e) positive depression or anxiety symptom screen using the PHQ-9 or PROMIS Pediatric Anxiety measures. **Exclusion Criteria.** Patients

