In the cross-sectional comparison of IBD patients with age-sex-matched controls, measures of psychophysiological and immune functioning and levels of anxiety, depressive, and disease symptoms will be summarized using standard descriptive statistics. Differences between groups (IBD vs. control) will be made using paired t-test or Wilcoxon signed rank tests to account for paired samples. Linear models will be used to examine the relationship between ANS and neuroimmune function with levels of anxiety, depression and disease symptoms. Specifically, models will include the main effect of group, the main effect of predictor (e.g., physiological reactivity or CRP), and the interaction between group and predictor. The interaction serves as the statistical test to determine if the correlation between predictor and outcome (e.g., anxiety, depression, etc.) differs between IBD patients and controls.

Intervention: Primary goals of the intervention are to establish the feasibility and acceptability of a RCT of enhanced biofeedback to improve autonomic reactivity and reduce levels of depression, anxiety and clinical symptoms in pediatric patients with IBD. Feasibility measures including consent rates, completion/retention rates, and treatment satisfaction ratings will be summarized using counts and percentages or means and standard deviations, as appropriate. Changes in clinical scores (anxiety, depression, and clinical symptoms) and autonomic reactivity from baseline, to end of treatment, and 2 months post treatment will be summarized within groups at each study time-point. The changes in the measures *within* and *across* groups will be analyzed using a two-factor repeated measures analysis of variance model

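### The IBD-versus-control tests use only complete 1:1 pairs, while the stated group sizes (60 and 40, total 120) do not add up; a model on all children would lose no one

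*Combined protocol and SAP*

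**What the plan says.** Section 11 introduces the analysis with "In the cross-sectional comparison of IBD patients with age-sex-matched controls" and then names the tests: "Differences between groups (IBD vs. control) will be made using paired t-test or Wilcoxon signed rank tests to account for paired samples". It goes on to linear models for the association of autonomic and immune measures with symptoms: "models will include the main effect of group, the main effect of predictor (e.g., physiological reactivity or CRP), and the interaction between group and predictor". No age, sex or matching term is listed for those models.

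The group sizes appear in the Table 1 caption (section 6, Wave 2 Recruitment): "n = 120; 60 IBD and 40 control at baseline". Section 8 gives a number for the patients only: "Requested sample size for Wave 2: 60 youth diagnosed with IBD; 10% refusal rate and 10% withdrawal rate expected". It describes controls by eligibility alone: "Control participants must meet all inclusion criteria excluding diagnosis with IBD or other chronic health condition".

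No section states a matching ratio, a pairing procedure, or what happens to unmatched children and incomplete pairs.

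**The concern.** A paired t-test works on within-pair differences, and so does the signed-rank test. A child without a partner contributes nothing, and neither does a child whose partner lacks the measurement. If the groups are 60 and 40, a third of the IBD patients would be recruited, assessed and then left out of the group comparison.

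Incomplete pairs are foreseeable whatever the control count. Section 6 says that clinic attendance has fallen and moves questionnaires to remote completion, but the physiological assessments belong to in-person visits and CRP needs a blood draw. Those measures are the likeliest to be missing.

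At stake is the precision of the estimated IBD-control differences in anxiety, depression, skin conductance, heart rate variability and CRP.

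**Working it through.** **Inputs.** From the Table 1 caption: 60 IBD, 40 control, total 120. From section 11: paired tests, matching on age and sex. The documents give no alpha, power, effect size, SD, within-pair correlation or baseline missing-data rate for this comparison. These are assumed below and varied. The 10% withdrawal in section 8 concerns the IBD samples and is not used as a baseline missing rate.

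**1. The plan's own total.** 60 + 40 = 100, not 120. Either 60 + 60 or 80 + 40 would give 120. With 1:1 matching the maximum number of pairs is the smaller group:

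- 60 and 40: 40 pairs, 20 of 60 IBD patients unused (33%).
- 60 and 60: 60 pairs, none unused.
- 80 and 40: 40 pairs, 40 unused.

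**2. Incomplete pairs.** If a fraction m of values is missing independently in each child, complete pairs = pairs × (1 − m)².

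| m (assumed) | of 40 pairs | of 60 pairs |
|---|---|---|
| 0% | 40 | 60 |
| 5% | 36.1 | 54.15 |
| 10% | 32.4 | 48.6 |
| 20% | 25.6 | 38.4 |

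**3. Paired test against a regression on age and sex.** Take SD = 1, let rho be the within-pair correlation and R² the share of variance explained by age and sex. Paired variance = 2(1 − rho)/pairs. Regression variance ≈ (1/n_IBD + 1/n_control)(1 − R²). Setting rho = R², the common factor cancels:

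- 40 controls, complete data: 2/40 = 0.0500 against 1/60 + 1/40 = 0.0417. The ratio is 0.83, or 17% smaller, equivalent to 2/0.0417 = 48 pairs instead of 40.
- 40 controls, 10% missing: 2/32.4 = 0.0617 against 1/54 + 1/36 = 0.0463. The ratio is 0.75, or 25% smaller.
- 60 controls, complete data: 2/60 = 0.0333 against 1/60 + 1/60 = 0.0333. No gain.
- 60 controls, 10% missing: 2/48.6 = 0.0412 against 1/54 + 1/54 = 0.0370. The ratio is 0.90, or 10% smaller.

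**4. If rho exceeds R².** The regression on 100 children and the test on 40 complete pairs are equally precise when rho = 1 − 0.833(1 − R²). That is rho = 0.21 at R² = 0.05, and 0.25 at R² = 0.10. Above that, a regression that ignores the pairing is less precise than the paired test.

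**5. A model that keeps the pairing and the unpaired children.** With 40 pairs plus 20 unpaired IBD patients, the generalised least-squares variance is (1 − rho)²/60 + (1 − rho²)/40. Divided by the paired variance 2(1 − rho)/40, this is (5 + rho)/6, which is below 1 for every rho below 1. Power is for an assumed 0.5 SD difference, two-sided 5%, normal approximation.

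| rho (assumed) | SE, 40 pairs | SE, all 100 | SE reduction | Power, 40 pairs | Power, all 100 |
|---|---|---|---|---|---|
| 0 | 0.2236 | 0.2041 | 9% | 60.9% | 68.8% |
| 0.2 | 0.2000 | 0.1862 | 7% | 70.5% | 76.6% |
| 0.5 | 0.1581 | 0.1514 | 4% | 88.5% | 91.0% |

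With 60 complete pairs, the paired test itself would have power 78.2%, 86.5% and 97.2% at these three correlations.

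**The case against.** A paired t-test or signed-rank test is a valid, standard analysis of matched pairs, and nothing here makes it biased. A reader might infer from the caption that 20 IBD patients will certainly be discarded. The documents do not support that: the same caption gives 120, which would mean 60 controls if the 60 IBD patients are right. It would be equally wrong to say that the loss is the same whatever the control count. With 60 controls and complete data it is zero, and the 10% figure then comes wholly from assumed missingness.

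A reader might also take this to be the study's main contrast. The Wave 2 objective in section 5 concerns associations of reactivity and CRP with symptoms, and the models that address them need no complete pairs. The follow-up models do not depend on the pairing either.

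Finally, the 17% and 25% figures assume that age and sex capture all that the matching captures. A non-linear age effect or another factor shared within pairs would shrink or reverse the gain of a plain regression (step 4).

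All of this stands as a limit on the point. Two things remain. First, the linear models do not stand in for the paired tests: with an interaction in the model, the group term is the difference at one value of the predictor, not the overall difference. Second, a model with a matched-set term removes the dependence on rho = R², because it uses the pairing where it exists (step 5).

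**Conclusion.** The point holds in conditional form. The caption does not add up, so the number of pairs cannot be known from the documents. With 40 controls matched 1:1, 20 of 60 IBD patients fall outside the test. A model on all 100 then has about 17% smaller variance if rho = R² (25% at an assumed 10% missing). A matched-set model has an SE about 4% to 9% smaller for rho from 0.5 to 0. With 60 controls the gain is 0% in variance with complete data and about 10% at 10% missing. The absence of a rule for incomplete pairs holds under either count.

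The cost is a moderate loss of precision in the simple group-difference tests only. It is worth correcting because the remedy is inexpensive, and section 11 already chooses a mixed model that uses all available outcome data for the intervention.

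**What to change.** 1. Reconcile the total of 120 with 60 + 40 in the Table 1 caption. State the number of controls in section 8, and give the matching ratio and pairing procedure.
2. Make the main group comparison a linear mixed model for each measure on group, age and sex, with a random effect for matched set where pairs exist. Use every child with data on that measure. Transform skewed measures.
3. Keep the paired t-test or signed-rank test on complete pairs as a sensitivity analysis, and report how many pairs it uses.

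Steps 2 and 3 change only the analysis wording. Step 1 requires the sponsor to settle the control count. No new data are needed. The small downside is that the model assumes a form for the age effect; age categories can be used if a linear term is doubtful.

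### The IBD-control linear models carry the group x predictor test but include neither the matched pair nor the matching variables, age and sex

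*Combined protocol and SAP*

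**What the plan says.** The comparison is set out in section 11 (Statistical analysis): "In the cross-sectional comparison of IBD patients with age-sex-matched controls", descriptive summaries come first. The group test is then given: "Differences between groups (IBD vs. control) will be made using paired t-test or Wilcoxon signed rank tests to account for paired samples".

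The same paragraph goes on to linear models relating autonomic and immune measures to anxiety, depression and disease symptoms. Their listed content is "models will include the main effect of group, the main effect of predictor (e.g., physiological reactivity or CRP), and the interaction between group and predictor". Of these terms, the last has an explicit role: "The interaction serves as the statistical test to determine if the correlation between predictor and outcome" differs between patients and controls.

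Table 1 (Wave 2) gives the sizes as "n = 120; 60 IBD and 40 control at baseline; IBD patients followed over 24 months". Section 8 defines controls only by eligibility ("Control participants must meet all inclusion criteria excluding diagnosis with IBD or other chronic health condition") and gives no matching ratio or procedure.

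Nothing else in section 11 fills the gap. The multi-level model in its opening paragraph is for adjustment at follow-up. The sentence on optional baseline covariates and the SAS MIXED statement belong to the intervention analysis.

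**The concern.** The plan recognises that matching has to be carried into the analysis, and does so for the simple group test. It then moves to models on the same children that contain neither of the two things that would carry it: a pair effect, or age and sex themselves. Three consequences are possible.

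- The group effect in the model gets a standard error that ignores the positive covariance between matched children.
- The interaction test, the only stated test of whether physiology relates to symptoms differently in IBD, leaves explainable outcome variance in the residual.
- If age or sex affects both the predictor (skin conductance, heart rate variability, CRP) and the outcome, the predictor slope mixes that shared dependence with the association of interest. Matching balances age and sex between groups. It does not remove their effect on a slope estimated within groups.

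**Working it through.** **Inputs.** From Table 1: 60 IBD and 40 controls, so at most 40 one-to-one pairs and at least 20 IBD patients without a match, unless controls are reused. The documents give no alpha, power, effect size, SD or within-pair correlation for this comparison, so there is no planned figure to reproduce. Assumed: two-sided 5% tests and a range of correlations. Let re be the within-pair correlation of the residual outcome and rx that of the predictor. For unrelated children matched exactly on age and sex, each is the share of variance that age and sex explain.

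**Counts.** 60 + 40 = 100, not 120. A total of 120 would fit 60 + 60.

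**Group effect.** With 40 pairs plus 20 unmatched patients and unit variance, the true variance of the mean difference is 1/60 + 1/40 - 2 x 40 x re/(60 x 40) = 0.0417 - 0.0333 re. The model as written uses 0.0417. Its standard error is therefore too large by the factor 1/sqrt(1 - 0.8 re): 1.09 at re = 0.2, 1.15 at 0.3, 1.29 at 0.5. Simulation of the full model gave 1.09, 1.14 and 1.28.

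**Interaction standard error.** With complete pairs the factor is about 1/sqrt(1 - re x rx), so it depends on the product of the two correlations. Simulated for 60 v 40:

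| re | rx | Reported / true SE | False-positive rate as written |
|---|---|---|---|
| 0.2 | 0.2 | 1.01 | 4.3% |
| 0.3 | 0.3 | 1.03 | 4.2% |
| 0.5 | 0.5 | 1.10 | 3.1% |
| 0.2 to 0.5 | 0 | 0.99 to 1.00 | 4.9% to 5.4% |
| 0.3 | -0.3 | 0.96 | 5.9% |

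**Interaction power, model as written -> with the pair modelled (60 v 40, re = rx).** Set A: 4,000 datasets, interaction 0.6 per SD, correlation estimated. Set B: 6,000 datasets, interaction 0.58, true correlation supplied, so its gains are upper bounds.

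| Correlation | Set A | Set B |
|---|---|---|
| 0.1 | difference 2 points or less | 77.1% -> 78.2% |
| 0.2 | 81% -> 82% | 77.8% -> 80.1% |
| 0.3 | 81% -> 85% | 79.2% -> 84.1% |
| 0.5 | 83% -> 93% | 80.0% -> 91.9% |

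With 60 v 60, Set B gives similar gains: 78.9% -> 81.4% at 0.2, 79.5% -> 85.1% at 0.3, 82.6% -> 93.7% at 0.5. With rx = 0 the standard error is essentially right but power is still lost (60 v 40, re = 0.5: 78.2% -> 86.6%). Much of the loss is therefore lost efficiency, not a misreported standard error.

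**Common slope.** Suppose age explains 20% of the variance of both predictor and residual outcome, in the same direction, and the true slope is zero. The slope induced without adjustment is sqrt(0.2) x sqrt(0.2) = 0.2 SD per SD. The standard error of the average of the two group slopes is about sqrt(0.25 x (1/60 + 1/40)) x sqrt(1 - 0.04) = 0.102 x 0.98 = 0.100. So z is about 2.0, and roughly half of such studies would reject a true null. Simulation agrees: false-positive rate 49% as written, 42% to 43% with a pair term only, 5.6% with age as a covariate. In that setting, interaction power for a true 0.6 was 83%, 84% and 89%; with 10% of variance explained it was 82%, 83% and 85%. If age acts equally in both groups, the induced slope is the same in each and cancels from the interaction. The confounding therefore falls on the common slope.

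**The case against.** The strongest reply is that little is lost on the interaction where it matters. Matching is on age and sex only, so a correlation of 0.5 would need those two variables to explain half the variance of predictor and outcome. At 0.2 or below the loss is about 1 to 3 points. This stands, and it limits the size of the point.

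A reader might infer that the interaction test as written is always conservative. It is not: its standard error is about right if the predictor is uncorrelated within pairs, and slightly too small if the product of the two correlations is negative.

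A reader might also expect the model's group coefficient, once the pair is modelled, to agree with the paired test. It need not. The paired test estimates the unadjusted mean difference among complete pairs. The coefficient is adjusted for the predictor, refers to one value of it, and uses unmatched patients as well.

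Nor do the documents show a decision to ignore pairing. The text lists terms the models will include and does not exclude others, so this is an omission.

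Finally, section 5 states the Wave 2 objective as associations in youth with IBD, without a control contrast, and section 8 requests no control sample size. The comparison is not the study's main aim. It is still planned, with a named test.

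**Conclusion.** The point holds as an under-specified model that is nearly free to improve. As written, the linear models drop matching that the same paragraph says must be accounted for, and leave age and sex unadjusted. The clearest effect on a standard error is on the group term: about 9% too large at a correlation of 0.2 and about 28% at 0.5. The loss of interaction power is about 1 to 3 points up to 0.2, about 4 to 5 at 0.3 and about 10 to 12 only at 0.5. The potentially larger issue is confounding of the common slope if age or sex drives both predictor and outcome. The 49% is an illustration of that under an assumed 20% shared variance, not a forecast.

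All of these sizes rest on assumed correlations and effects; only the 60 and 40 come from the plan. They do not support calling the interaction test invalid.

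**What to change.** In section 11, state that the IBD-control linear models include age and sex as covariates in addition to group, predictor (centred) and group x predictor, optionally with a random intercept for the matched pair. State that IBD patients without a matched control stay in the model. Age and sex adjustment is the essential part, because a pair intercept alone leaves most of the slope confounding in place.

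Reconcile the control count and the matching ratio: Table 1 lists 60 and 40 under n = 120. With 40 controls, a one-to-one paired test sets aside at least 20 IBD patients, whereas the model can keep them.

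The cost is a sentence or two of analysis text, a pair identifier in the dataset if the random intercept is used, and one degree of freedom each for sex and linear age. If age and sex explain nothing, about 1 point of power is lost. Age and gender are already on the demographics questionnaire, so no new data or participants are needed.

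### The group-by-predictor interaction in the IBD-versus-control comparison tests a difference in slopes, but the plan reads it as a test of whether correlations differ

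*Combined protocol and SAP*

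**What the plan says.** Section 11 (Statistical analysis), in the paragraph on the cross-sectional comparison, introduces the analysis this way: "Linear models will be used to examine the relationship between ANS and neuroimmune function with levels of anxiety, depression and disease symptoms". It then lists the terms, which are a group effect together with "the main effect of predictor (e.g., physiological reactivity or CRP), and the interaction between group and predictor". Next comes a sentence on what the product term is for: "The interaction serves as the statistical test to determine if the correlation between predictor and outcome" is different in IBD patients and controls.

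The paragraph does not mention standardising within group, a variance model, or a direct comparison of two correlation coefficients. The check of modelling assumptions in section 11 stands in the intervention text, not here. Pairing is used for the simple group differences ("Differences between groups (IBD vs. control) will be made using paired t-test or Wilcoxon signed rank tests to account for paired samples") and is not carried into the linear models.

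Section 8 defines the comparison group: "Control participants must meet all inclusion criteria excluding diagnosis with IBD or other chronic health condition". Table 1, under Wave 2 Recruitment, gives the sizes as "n = 120; 60 IBD and 40 control at baseline".

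**The concern.** In a linear model the product term estimates how much the change in outcome per unit of predictor differs between groups. That is not a difference in correlations. Within each group,

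slope = correlation × SD(outcome) / SD(predictor).

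The eligibility rules make unequal predictor spread plausible for CRP, which the plan itself names as an example predictor. One group is newly diagnosed with an inflammatory disease and the other has no chronic condition.

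What is at stake is the sentence the study may write afterwards. Read literally, the plan allows a significant interaction to be reported as a difference in correlation when none exists, and a null interaction to be reported as similar correlations when they differ. This bears on the Wave 2 objective in section 5, which concerns how reactivity and CRP relate to anxiety, depressive and disease symptoms.

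**Working it through.** The plan gives no alpha, SD, expected correlation or power for this analysis, so there is no stated figure to reproduce.

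**Inputs**
- From the documents: 60 IBD and 40 controls (Table 1). The same line also says 120, although 60 + 40 = 100, so other sizes were tried.
- Assumed: two-sided alpha 0.05; common correlation r from 0 to 0.5; predictor SD in IBD k times that in controls; equal outcome SDs, set to 1; normal data; independent groups.

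**Closed form when correlations are equal.** With control predictor SD 1 and IBD predictor SD k, the slopes are r and r/k.
- Slope difference = r(1 − 1/k)
- SE = √[(1 − r²)(1/(60k²) + 1/40)]
- For k = 2, the second bracket is 1/240 + 1/40 = 0.02917.
- r = 0.3: difference 0.15; SE = √(0.91 × 0.02917) = 0.163; ratio 0.92; rejection probability Φ(0.92 − 1.96) + Φ(−0.92 − 1.96) ≈ 15%.
- r = 0.5: difference 0.25; SE = √(0.75 × 0.02917) = 0.148; ratio 1.69; rejection probability ≈ 39%.

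**Simulation of the same setting** (20,000 data sets per cell, ordinary least squares, 60/40). Rejection rate of the interaction with equal true correlations:

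| r | k = 1.5 | k = 2 | k = 3 | k = 5 |
|---|---|---|---|---|
| 0 | 5% | 5% | 5% | 5% |
| 0.1 | 5.0% | 6.2% | 6.8% | 7.8% |
| 0.2 | 6.5% | 8.9% | 13.0% | 17.0% |
| 0.3 | 8.9% | 14.1% | 23.7% | 34.0% |
| 0.4 | 12.6% | 23.3% | 40.7% | 55.9% |
| 0.5 | 18.1% | 36.7% | 62.4% | 79.2% |

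The closed form agrees within about 3 points. A Fisher-z comparison of the two correlations stays between 4.6% and 5.4% in the equal-correlation settings. At k = 2, other group sizes give 18.6% (r = 0.3) and 50.4% (r = 0.5) with 60/60, and 15.5% and 40.3% with 120/40.

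**Equal slopes, equal residual SD, unequal predictor spread.** Take slope 0.3 and residual variance 0.91 in both groups. At k = 2 the IBD correlation is 0.6/√(0.36 + 0.91) = 0.53, against 0.30 in controls. The interaction rejects 5.1% and Fisher z 26.5%. At k = 3 the correlations are 0.69 and 0.30, and the rates are 5.1% and 71.1%.

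**Outcome spread that rises with predictor spread.** If it rises fully in step, slopes and correlations are both equal. At r = 0.3 the interaction then rejects 2.4% (k = 1.5) and 0.7% (k = 2). With a partial rise (outcome SD 1.25 times and predictor SD 3 times larger in IBD), rejection is still 12.1% at r = 0.3 and 39.3% at r = 0.5.

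**Standard errors.** The rates below 5% arise because one pooled residual variance is applied to groups with different residual spread. With equal slopes and an IBD residual SD 1.5 to 2 times larger, the pooled test rejects 0.4 to 4%. Robust standard errors bring it back to about 5%.

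**The case against.** The strongest reply is that *correlation* is used loosely here. The same paragraph speaks of a relationship, section 5 speaks of associations, and no Pearson coefficient is specified anywhere. On that reading the plan describes an ordinary moderation model, and the slope comparison is a sound choice. Much of this stands, and it is why the model should stay. It does not dispose of the point. The sentence fixes the conclusion to be drawn, and the plan does not say whether effect per unit or strength of association is meant; the two can disagree in either direction.

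Three stronger readings are tempting, and the documents do not support them.

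- **Unequal predictor spread alone inflates the test.** It does not. The rate is 5% at r = 0, at most about 8% at r = 0.1, and about 5% when slopes and residual SDs are equal. Inflation needs a common non-zero correlation together with outcome spread that does not keep pace with predictor spread.
- **The excess rejections are type I errors of the planned model.** They are not. In those settings the slopes truly differ, so rejecting equal slopes is correct. The error lies only in calling the result a difference in correlation.
- **The interaction should give way to Fisher z or within-group standardisation.** Those methods reject when only the spread differs. With equal slopes, Fisher z rejects about 27% to 99% of the time for SD ratios of 2 to 5.

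It is also fair to say that unequal spread is inferred from the eligibility rules for CRP only. The documents give no comparable reason for skin conductance or heart rate variability.

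**Conclusion.** The concern holds in this limited form: section 11 names the wrong quantity. The interaction tests slopes, and it matches a test of correlations only if the ratio of outcome SD to predictor SD is the same in both groups.

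Under equal correlations, equal outcome SDs and a twofold predictor SD ratio at 60/40, the conclusion as worded would be wrong about 14 to 15% of the time at r = 0.3 and 37 to 39% at r = 0.5, instead of 5%. Under equal slopes the interaction stays at about 5% and can miss correlations of, for example, 0.53 and 0.30.

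These figures illustrate what could happen; they do not predict this study's error rate. Alpha, correlations, SDs, normality and independence of the groups are all assumed. The model itself is not at fault. What needs correcting is the inference attached to it.

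**What to change.** Keep the model with group, predictor and their product, and make three changes in section 11.

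1. State that the interaction tests whether the slope, meaning the change in outcome per unit of predictor, differs between IBD patients and controls. Add that a difference in correlations will not be concluded from the interaction alone.
2. Specify heteroscedasticity-robust standard errors, in a form suited to small samples such as HC3.
3. Report for each group the SDs of predictor and outcome and the within-group correlation with a 95% confidence interval, so that readers can see whether a slope difference reflects spread, strength of association, or both.

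Fisher z or within-group standardisation should not become the main test. The cost is one reworded sentence, one option in the model code and a few descriptive statistics. No new data are needed.
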